IRAS Project ID: **227870**

11. [name] (SpR Anaesthesia)

12. [name] (ICU Clinical Fellow)

STUDY SUMMARY

STUDY OVERVIEW	
Full title	The impact of systemic pH on cardiac function and clinical outcome in the critically ill patient
Objectives	Hypothesis Titration studies in animals with normal cardiac function show that a reduction in blood pH (and presumably that of the intracellular and interstitial compartments) from the normal level of 7.40 to 7.20 is associated with a rise in cardiac output. However, when blood pH is less than 7.20, cardiac output is reduced. Similar studies in humans with or without normal cardiac function have not been done, and yet blood pH at which aggressive treatment is recommended has been set at 7.20 based solely on animal experiments. We hypothesize that a change in blood pH in humans will also affect cardiac function, but the level of blood pH at which this is observed might be similar or different in humans. In addition, the presence or absence of

Full title of the research: **The impact of systemic pH on cardiac function and clinical outcome in the critically ill patient.**

IRAS Project ID: **227870**

	
underlying cardiac disease and the type of acid-base abnormality present might modify the response of the heart to changes in blood pH.
 
Goals
 
Primary
 
 1. Assess whether there are significant changes in cardiac function associated with changes in blood pH. 2. Relate the changes in cardiac function to presence or absence of underlying cardiac disease. 
Secondary
 
 3. To establish which factors affected by blood pH have an impact on cardiac function. 4. Study the mortality of patients admitted to the Intensive Care Unit (ICU) who had continuous cardiac monitoring at any time during their admission and relate it to changes in blood pH.
Type of trial	It is not a trial
Trial design and methods	It is not a trial
Health condition(s) or problem(s) studied	It is not a trial
Target sample size	Taking into account that the primary objective of the study is to

Full title of the research: **The impact of systemic pH on cardiac function and clinical outcome in the critically ill patient.**

IRAS Project ID: **227870**

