1 INTRODUCTION

Why?

We would like to perform an analysis of the relationship between systemic pH and cardiac function and clinical outcome in critically ill patients in patients hospitalized the Intensive Care Unit.

How is it of relevance and importance to patients and public?

Studying this subject we could provide important information about the impact of systemic pH on cardiac function and clinical outcome in seriously ill patients and enable the clinician to

Full title of the research: **The impact of systemic pH on cardiac function and clinical outcome in the critically ill patient.**

IRAS Project ID: **227870**

understand the best treatment of these patients. Patients will be studied who had cardiac monitoring during their ICU admission and an acid-base metabolic disorder. We exclude those patients with cardiac history or who presented an acute coronary syndrome during ICU admission.

IT IS NOT A THERAPEUTIC STUDY. ONLY OBSERVATIONAL. NO INTERVENTIONS.

Where?

In seven different ICU's between King's College NHS Foundation Hospital and Lewisham and Greenwich NHS Trust

How?

The study will take approximately six month to collect prospectively data from each unit. The data will be extracted from the medical notes and ICU charts. No active involvement with participants.

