2 BACKGROUND AND RATIONALE

3 OBJECTIVES

Goals

Primary

1. Assess whether there are significant changes in cardiac function associated with changes in blood pH.
2. Relate the changes in cardiac function to presence or absence of underlying cardiac disease.

Secondary

3. To establish which factors affected by blood pH have an impact on cardiac function.

Full title of the research: **The impact of systemic pH on cardiac function and clinical outcome in the critically ill patient.**

IRAS Project ID: **227870**

4. Study the mortality of patients admitted to the Intensive Care Unit (ICU) who had continuous cardiac monitoring at any time during their admission and relate it to changes in blood pH.

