The comparison between a polytomic predictor and a quantitative response is made through the analysis of variance (ANOVA) in the case of meeting the conditions of normality and homogeneity of variances. If any of these conditions is not met, it is done with the non-parametric H test of Kruskal-Wallis. If the polytomic predictor is ordinal, the ANOVA trend test or the non-parametric Jonckheere-Terpstra trend test is also used, depending on whether normality is met or not, respectively.

Full title of the research: **The impact of systemic pH on cardiac function and clinical outcome in the critically ill patient.**

IRAS Project ID: **227870**

The relationship between two independent quantitative variables is evaluated with the correlation coefficient r of Pearson if normality is met, or with the nonparametric correlation coefficient ρ of Spearman if normality is not met. Its graphic representation is made with the scatter diagrams or points.

Normality is assessed with the Kolmogorov-Smirnov test with the Lilliefors significance correction for large samples, or with the Shapiro-Wilks test for small samples. The equality of variances is analyzed with the Levene variance homogeneity test.

The relationship between two related quantitative variables is performed using the Student-Fisher t-test for related samples in case the normality condition is met. Otherwise, the non-parametric Wilcoxon T test is used. The relationship between two paired categorical variables is performed by the McNemar symmetry test.

The relationship between a continuous quantitative response and one or several predictors, whether binary, polytomic or quantitative, is done with Simple or Multiple Linear Regression respectively.

The polytomous predictors variables are introduced in the Linear Regression models broken down into binary indicator variables coded with respect to the first reference category.

An estimative multivariate linear regression model of the effect of the predictor Change of pH (between the lowest and highest pH) on the response Change in cardiac output

Full title of the research: **The impact of systemic pH on cardiac function and clinical outcome in the critically ill patient.**

IRAS Project ID: **227870**

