The relationship between two independent quantitative variables is evaluated with the correlation coefficient r of Pearson if normality is met, or with the nonparametric correlation coefficient ρ of Spearman if normality is not met. Its graphic representation is made with the scatter diagrams or points.

Full title of the research: **The impact of systemic pH on cardiac function and clinical outcome in the critically ill patient.**

IRAS Project ID: **227870**

Normality is assessed with the Kolmogorov-Smirnov test with the Lilliefors significance correction for large samples, or with the Shapiro-Wilks test for small samples. The equality of variances is analyzed with the Levene variance homogeneity test.

The relationship between two related quantitative variables is performed using the Student-Fisher t-test for related samples in case the normality condition is met. Otherwise, the non-parametric Wilcoxon T test is used. The relationship between two paired categorical variables is performed by the McNemar symmetry test.

The relationship between a continuous quantitative response and one or several predictors, whether binary, polytomic or quantitative, is done with Simple or Multiple Linear Regression respectively.

The polytomous predictors variables are introduced in the Linear Regression models broken down into binary indicator variables coded with respect to the first reference category.

An estimative multivariate linear regression model of the effect of the predictor Change of pH (between the lowest and highest pH) on the response Change in cardiac output (corresponding to the moments between the lowest and the highest pH) has been performed. The possible role as confounding factors of several variables on this relationship has been evaluated. A predictive multivariate model of linear regression has been performed to evaluate the factors that intervene in the Cardiac Contractility.

Full title of the research: **The impact of systemic pH on cardiac function and clinical outcome in the critically ill patient.**

IRAS Project ID: **227870**

Both the predictive and the estimative models have been carried out with the manual backward step procedure using the criterion of decreasing statistical significance to establish the order to evaluate the withdrawal or permanence of each predictor.

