In the multivariate predictive linear regression model, the criterion of statistical significance was used to decide the maintenance or withdrawal of the predictors in each step. They remain in the model if they are significant and are removed from the model if they are not significant.

In the multivariate models of linear regression, the criterion of clinical significance has been used to decide on the maintenance or withdrawal of the predictors in each step. They remain in the model if they produce a change greater than 10% in the coefficient of the predictor of interest (presence of confounding bias) and withdraw if the change is less than 10% (absence of confounding bias).

The conditions of application of the simple or multiple linear regression (linearity, independence, normality and equality of variances) are evaluated by analysing the residuals.

Values of $P < 0.05$ are considered significant. The statistical treatment has been performed the statistical package SPSS, version 18 (SPSS Inc, Chicago, IL, USA).

Full title of the research: **The impact of systemic pH on cardiac function and clinical outcome in the critically ill patient.**

IRAS Project ID: **227870**

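### The single lowest-to-highest pH difference discards the pH level, so on the plan's own turning curve effects can cancel or the slope can change sign with case mix

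*Combined protocol and SAP*

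**What the plan says.** The Objectives row of the Study Summary describes animal data in which cardiac output rises as pH falls from 7.40 to 7.20. It continues: "However, when blood pH is less than 7.20, cardiac output is reduced". For humans, it says that "the level of blood pH at which this is observed might be similar or different in humans", and it notes that "blood pH at which aggressive treatment is recommended has been set at 7.20 based solely on animal experiments". The first primary goal in Section 3 is: "Assess whether there are significant changes in cardiac function associated with changes in blood pH".

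No model is labelled primary. The only one that names pH as the predictor of interest appears in the Study Summary, Section 4 and Section 8. It is a linear regression estimating "the effect of the predictor Change of pH (between the lowest and highest pH) on the response Change in cardiac output". Each patient contributes one pH difference and one output difference. The confounders are not named, and no lowest pH, baseline pH, curve, knot or interaction is specified. A second regression, for contractility, is predictive and lists no predictors.

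On model checking, Section 8 says: "The conditions of application of the simple or multiple linear regression (linearity, independence, normality and equality of variances) are evaluated by analysing the residuals". It gives no action if linearity fails. On who is studied, Section 1 says: "Patients will be studied who had cardiac monitoring during their ICU admission and an acid-base metabolic disorder". Neither that sentence nor the criteria in Sections 7.1 and 7.2 restrict the pH range.

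**The concern.** The hypothesis is about the level of pH at which the response changes. The model uses only the distance between two levels. If the response rises on one side of a turning point and falls on the other, equal distances carry opposite expected effects and the fitted slope becomes an average over whichever patients were enrolled.

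If the human curve turns inside the observed range, three things follow:

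- A real relation can be missed.
- Two cohorts with the same physiology can report significant slopes of opposite sign.
- A significant slope says nothing about the pH level that the protocol itself says rests on animal work alone.

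The non-parametric fallback, Spearman's coefficient, is monotone and has the same limitation.

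**Working it through.** Convention: x = highest pH minus lowest pH (the fall); y = output at the lowest pH minus output at the highest. A positive slope means that output rises as pH falls.

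**The plan's sample size.** For one correlation, n = ((1.960 + 0.842)/atanh(r))² + 3. With r = 0.15, two-sided 5% and 80% power, this gives 346.6, which matches the plan's 346. The printed coefficient of 1.5 is not a possible correlation; 0.15 is assumed here. Below, n = 346.

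**Step 1: arithmetic on the protocol's curve.** Take a peak at 7.20 with slope b on each side, so y = b(|high − 7.20| − |low − 7.20|).

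- 7.20 to 7.40: x = 0.20, y = b(0.20 − 0) = +0.20b
- 7.10 to 7.30: x = 0.20, y = b(0.10 − 0.10) = 0
- 7.00 to 7.20: x = 0.20, y = b(0 − 0.20) = −0.20b

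The opposite signs in the first and third lines need neither a value for b nor symmetry.

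**Step 2: mixing patients.** If a share s moves only below 7.20 and the rest only above it, with the same spread of x, the expected slope is b(1 − s) − bs = b(1 − 2s). For s = 0, 0.25, 0.5, 0.75 and 1 this is +b, +0.5b, 0, −0.5b and −b. A simulation with b = 1 and noise SD 0.10 returned these values; at s = 0.5 the slope was significant in 5.6% of runs. The mean of y is then flat in x, so a check of linearity in x looks satisfied.

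**Step 3: power.** All inputs are assumptions: symmetric turn at 7.20, 5 L/min per pH unit, residual SD 1.5 L/min, highest pH normal (mean 7.40, SD 0.03), 3000-4000 runs per setting. The line is the t test of the single slope. The alternative is a 2-df F test of the pH change split at 7.20.

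| Lowest pH | Line | Two terms |
|---|---|---|
| uniform 7.00-7.40 | 6-7% | 95% |
| uniform 7.05-7.35 | 9% | 82% |
| uniform 7.10-7.40 | about 80% | 92% |
| uniform 7.20-7.40 | 97% | 97% |
| normal, mean 7.25, SD 0.08 | 67% | 91% |
| normal, mean 7.30, SD 0.08 | 92% | 93% |

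Repeat runs agreed to within about 2 percentage points. With no effect, both tests rejected in 5.0-5.2% of runs. In the first row the mean correlation is 0.02 in size, Spearman's power is 6.6%, and the two-term slopes are +5.0 (SE 1.4) above and −5.0 (SE 1.5) below.

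Varying the first row, line v two terms:

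- SD 1.0: 8% v 100%
- SD 2.0: 6% v 74%
- slope 2.5: 5% v 39%

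The line recovers when symmetry is broken. It has 99% to nearly 100% power with the turn at 7.30 or 7.10, 86% with the slope below 7.20 doubled, and 52% with it halved.

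**Step 4: sign.** On the Step 3 curve, the line's mean slope is +2.6 for lowest pH 7.10-7.40, +0.2 for 7.00-7.40, −1.6 for 7.00-7.30 and −2.9 for 6.90-7.30 (99% power). A second set of runs (b = 1, noise SD 0.10, highest pH SD 0.05, lowest pH SD 0.08) gave −0.43, −0.06, +0.25 and +0.79 for mean lowest pH 7.00, 7.15, 7.20 and 7.30. With the lower slope doubled, the sign changes between 7.20 and 7.25; with it halved, between 7.05 and 7.10.

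**Step 5: highest pH also varies** (fall 0.05-0.35). For highest pH 7.20-7.50, power is 37% for the line, 41% for a quadratic in the difference and about 100% for the two terms. For 7.30-7.50 it is 5%, 36% and 99.7%. A curved term in the difference alone is therefore not a cure.

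**The case against.** The strongest reply is that the plan also lists a paired t test, and output at the lowest and highest pH forms a pair. Under the Step 3 assumptions that test has about 100% power for lowest pH 7.00-7.40 and 99% for 6.90-7.30, and the mean change is positive in all four sign-flip cohorts (+0.38 to +0.59 L/min). So the risk of opposite conclusions belongs to the slope, not to every listed analysis. That stands. But the plan does not assign the paired test to this goal, and the test cannot relate response to the size or level of the pH change. It falls to 66% when highest pH is 7.20-7.50 and to 26-31% with the turn at 7.30.

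Second, the residual check would often show curvature in the near-worst case, where highest pH is close to fixed: a quadratic term is significant in 81% of runs. When highest pH varies, this drops to 22-46%, and no remedy is stated in either case.

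Third, the size is wholly assumed, several settings show little or no loss, and none of the four goals asks for a threshold. All true. These points limit any claim about how much is lost in this cohort, but they leave Step 1 untouched.

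Fourth, a knot at the animal value may be wrong. With a true turn at 7.10, the 7.20 knot keeps 99.9% joint power but gives slopes of +5.7 and +1.1 instead of +5 and −5. That is a real cost and calls for a sensitivity analysis.

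Finally, no covariates are named at all, so lowest pH is neither included nor ruled out.

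**Conclusion.** The concern holds. On the response shape that motivates the study, the specified model gives the same predictor value to patients with opposite expected responses, and nothing in the plan restores the pH level. That conclusion rests on the documents and simple arithmetic.

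The size rests on assumed slopes, noise and pH distributions. It runs from no loss, when lowest pH stays at 7.20-7.40, to almost complete loss of power when values are spread evenly around the turn. In between, the slope's sign follows case mix. The sponsor cannot know in advance which situation will apply. The model should be changed before analysis.

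**What to change.** Keep the within-patient change model, and replace the single pH change by two pre-specified terms that sum to it:

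- above = max(high, 7.20) − max(low, 7.20)
- below = min(high, 7.20) − min(low, 7.20)

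Keep both terms in the model whatever the backward steps do. Test them jointly on 2 df and report both slopes with 95% confidence intervals. Retain the single slope as a secondary analysis.

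The knot at 7.20 comes from the protocol's own hypothesis and is an analysis choice, not a statement about treatment. Pre-specify a sensitivity analysis that repeats the model with knots at 7.10, 7.15, 7.25 and 7.30, or uses the difference in a restricted cubic spline of pH (3 knots, 2 df; 85% power in the 7.00-7.40 setting). Report all of these without choosing by p-value. If a mixed model on pH levels is preferred, include each patient's mean of the pH terms so that within- and between-patient effects are separated.

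The cost is SAP wording and one degree of freedom in an ordinary linear regression, with a small power loss if nearly all values lie on one side. No data are needed beyond the two pH values and matching outputs already planned. If no value lies below 7.20, the lower term is zero for everyone and the model is the planned line.

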4 STUDY DESIGN

- Study population and groups: those patients on haemodynamic monitoring in ICU (PiCCO monitoring)
- **Calculation of the sample size:**

Taking into account that the primary objective of the study is to analyze the relationship between the quantitative variables: change in pH and change in Cardiac Contractility, assuming an alpha risk of 5% (95% confidence level), a 20% beta risk (power of 80%) and a minimum ratio that has an estimated clinical significance with a correlation coefficient of 1.5, a bilateral estimate of sample size of 346 subjects is obtained. Assuming a 5% loss (17 individuals) during the study a total of 363 cases would be necessary.

- **Statistical methods:**

The description of quantitative variables is carried out with central tendency and dispersion indices, whether based on values (mean and standard deviation) or on ordinations (median and interquartile range) according to whether they meet normality or not, respectively. Its graphic representation is done with Histograms and Cash Diagrams. The description of categorical variables is performed with absolute and relative frequencies in percentages. Its graphic representation is done with bar charts.

Full title of the research: **The impact of systemic pH on cardiac function and clinical outcome in the critically ill patient.**

IRAS Project ID: **227870**

The relationship between categorical variables is analyzed by comparing proportions with the Pearson Chi-square test, provided that there are less than 20% of squares in the contingency table with expected frequencies less than 5. In the case that there is more 20% of squares with expected frequencies less than 5, the Fisher's exact test is used bilaterally.

The magnitude of the effect of the relationship between two binary variables has been analyzed with the Ratios of proportions or Relative Risk and with the Odds Ratio.

The relationship between a binary exposure variable and a quantitative response is analyzed with the Student-Fisher t test for independent samples if the normality condition is met. According to whether or not the equality of variances are met, the Student-Fisher t test is used for independent groups for homogeneous variances or for non-homogeneous variances, respectively. In case of not fulfilling the condition of normality, the comparison of two means is made with the non-parametric Mann-Whitney U test.

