5 STUDY SCHEDULE

Approximately:

- April 2018: Start collecting data from patient already in the ICU with the inclusion criteria.
- April 2018- September 18 approximately until reach the minimum number of 360 patients
- October-November 18 data analysis

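### The 10% confounding rule is applied across manual backward steps with no fixed patient set and no missing-covariate method, so a change of patients can be read as confounding

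*Combined protocol and SAP*

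**What the plan says.** Section 8 (Statistical Methods) describes two multivariable linear regressions. The estimative model relates change in pH to change in cardiac output. The predictive model looks for factors that affect cardiac contractility. On how they are built it says: "Both the predictive and the estimative models have been carried out with the manual backward step procedure", with predictors considered for removal in order of statistical significance.

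The retention rules differ. The predictive model keeps what is significant. The other rule refers to a predictor of interest and so belongs to the estimative model: "They remain in the model if they produce a change greater than 10% in the coefficient of the predictor of interest". The plan labels a larger shift as confounding bias and a smaller one as its absence.

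The candidate confounders are neither listed nor counted: "The possible role as confounding factors of several variables on this relationship has been evaluated". On the data source, section 1 says: "The data will be extracted from the medical notes and ICU charts". The only allowance for incomplete data is in the sample size paragraph of section 4: "Assuming a 5% loss (17 individuals) during the study a total of 363 cases would be necessary".

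The same statistical text appears in the Study Summary, section 4 and section 8. None of the three gives a missing-data rule, an imputation method, a common analysis set across steps, or an expected level of missingness.

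**The concern.** A change-in-coefficient rule measures confounding only if the fits with and without the covariate use the same patients. Covariates taken from routine notes and charts will plausibly have gaps. An ordinary regression run leaves out any patient who lacks a value for a covariate in the model. When a covariate with gaps is removed by hand and the model is rerun, the patients it had excluded come back. The pH coefficient then moves for two reasons, the loss of adjustment and the change of patients, and the 10% rule cannot tell them apart.

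Two things are at stake. Covariates may be kept, or true confounders dropped, because of who happened to have data. And the adjusted pH estimate may rest on fewer patients than the study planned for.

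**Working it through.** **Inputs.** From section 4: two-sided 5% alpha, 80% power, 346 patients, 5% loss (17), total 363. From section 8: manual backward steps and the 10% rule. Not given, and therefore assumed over a range: missingness per covariate and number of covariates.

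**1. The plan's own figure.** Section 4 prints "a correlation coefficient of 1.5, a bilateral estimate of sample size of 346 subjects is obtained". A correlation cannot be 1.5. With 0.15, the Fisher z formula gives

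n = ((1.960 + 0.842) / atanh(0.15))² + 3 = (2.802 / 0.1511)² + 3 = 346.6,

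which matches 346. The one-sided version gives 273.6, which does not. So 346 corresponds to a smallest effect of r = 0.15, and this is used below. The loss allowance is 346 × 0.05 = 17.3, taken as 17, and 346 + 17 = 363.

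**2. How often the 10% rule misfires.** Simulation: n = 346; standardised pH change and outcome with true correlation r; one covariate unrelated to either, missing completely at random. The pH coefficient is compared before and after the covariate is removed.

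| Missing | r = 0.15, patients change | r = 0.15, same patients | r = 0.30, patients change |
|---|---|---|---|
| 1% | about 7% | about 1–2% | about 0.1% |
| 3% | about 17% | about 1–2% | about 1% |
| 5% | about 26% | about 1–2% | about 3% |

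Entries are the share of runs with a shift above 10%. The covariate confounds nothing, so every such shift is false.

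An approximation shows why. The relative shift caused by the change of patients alone has standard deviation √(1/n₁ − 1/n) × √(1 − r²) / r, where n₁ is the number of complete records. At 5% missing, n₁ = 346 × 0.95 = 328.7 and the first factor is 0.0123.
- r = 0.15: 0.0123 × 0.989 / 0.15 = 0.081, so a 10% shift is only about 1.2 standard deviations away.
- r = 0.30: 0.0123 × 0.954 / 0.30 = 0.039, so it is about 2.5 standard deviations away.

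**3. The opposite error.** With a true confounder at r = 0.15, changing the patients led to its removal in roughly 2–11% of runs in which the fixed set would have kept it. This depends on the assumed strength of the confounder and is indicative only.

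**4. Patients left in the full model.** With k covariates each missing independently in a share m, complete records = 363 × (1 − m)^k:
- m = 1%, k = 3: 363 × 0.970 = 352
- m = 1%, k = 5: 363 × 0.951 = 345
- m = 2%, k = 5: 363 × 0.904 = 328
- m = 5%, k = 5: 363 × 0.774 = 281

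These assume that all 363 patients have pH and outcome data. The full model drops below 346 once more than 17 of 363 (4.7%) lack any needed value. Section 5 plans recruitment "until reach the minimum number of 360 patients"; if 5% of 360 were lost, 342 would remain before any covariate gap.

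**The case against.** The strongest objection is that the documents do not describe the faulty procedure. A reader might infer that the plan refits each step on whoever has data for the remaining covariates. It does not say so; it is silent. The misfire depends on separate runs with incomplete patients dropped. That is the natural result of manual steps with no stated rule, but it remains an inference.

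A reader might also infer that the first models must fall below 346. The documents do not support that. They give neither the number of covariates nor the missingness, and the 363 target holds 17 spare patients: three covariates at 1% missing leave 352. Counting every item on the data form as a candidate gives much larger losses, but no section names those items as candidates. The 346 was also set for an unadjusted correlation with contractility, whereas the estimative model's response is cardiac output, so it is only a rough benchmark.

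The misfire is worst when the effect is small and nearly vanishes at moderate correlations. Keeping a noise covariate under this missingness mechanism costs some precision but does not bias the pH estimate. The 10% argument does not reach the predictive model, although a shifting patient set would alter its p-values.

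All of this stands, and it limits the size and certainty of the point. It does not supply the missing rule. r = 0.15 is the effect the study was sized to detect, so the unfavourable case is a relevant one.

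**Conclusion.** The point holds in conditional form. The plan sets a 10% rule that is valid only on a common patient set, and it neither fixes that set nor says how missing covariates are handled. If the steps are run as ordinary complete-case regressions, false confounding calls for one noise covariate rise from about 1–2% to about 7%, 17% and 26% at 1%, 3% and 5% missing, for r = 0.15 and n = 346. At r = 0.30 they are about 0.1%, 1% and 3%. The figures rest on reading 1.5 as 0.15 and on values missing completely at random. A shortfall of patients in the adjusted model is possible, but its size cannot be settled from the documents; 328 of 363 with five covariates each 2% missing is an illustration. This should be corrected before analysis, because it makes a stated rule unreliable and the correction is cheap.

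**What to change.** In section 8, and in the matching text of the Study Summary and section 4:

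- State that every backward step and every 10% comparison in the estimative model is run on one analysis set fixed before modelling, and that the predictive model's steps also use one fixed set.
- Handle missing covariates by multiple imputation, with pH change and the outcome in the imputation model. Apply the 10% rule to pooled coefficients.
- Report the complete-case fit as a sensitivity analysis.
- List the candidate covariates, so that the imputation model and the starting model are defined in advance.

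The two main parts do different jobs. The fixed set removes nearly all the false shifts; imputation recovers the patients that the full model would otherwise lose. The cost is wording and modest extra programming, including pooling at each manual step. No new data are needed.

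### The predictive model of contractility names as a factor any predictor that survives backward deletion at P<0.05, with no prespecified candidates, multiplicity control or internal validation

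*Combined protocol and SAP*

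**What the plan says.** Section 8 (repeated in section 4 and in the study summary) plans two multivariable linear regressions. One estimates the effect of change in pH on change in cardiac output. The other is the subject of this point: "A predictive multivariate model of linear regression has been performed to evaluate the factors that intervene in the Cardiac Contractility".

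Both use a "manual backward step procedure using the criterion of decreasing statistical significance to establish the order to evaluate the withdrawal or permanence of each predictor". For the predictive model the decision at each step is by P value alone: "They remain in the model if they are significant and are removed from the model if they are not significant". The threshold is general: "Values of $P < 0.05$ are considered significant".

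A second rule keeps a variable if it moves the coefficient of the predictor of interest by more than 10%. That rule is about confounding of a chosen exposure. The predictive model has no such exposure, so the rule does not govern it.

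The closest objective is goal 3 in section 3, which is secondary: "To establish which factors affected by blood pH have an impact on cardiac function".

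The documents give no list or maximum number of candidates for this model, no adjustment for multiple testing, no shrinkage and no internal validation. The only check named is analysis of residuals.

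**The concern.** The rule tests every candidate at 0.05 and reports those that pass. With several candidates, some will pass by chance, and the plan's wording then treats them as factors that act on the heart. A reader of the results could not tell how many were tried, and so could not discount for chance. The fit of the final model, measured on the data that chose its terms, would also look better than it is.

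At stake is goal 3. This model is the only analysis the plan names for finding factors that affect cardiac function, and section 1 hopes that the study will inform treatment.

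**Working it through.** **Sample size used.** Section 4 assumes "assuming an alpha risk of 5% (95% confidence level), a 20% beta risk (power of 80"%) and a "correlation coefficient of 1.5, a bilateral estimate of sample size of 346 subjects is obtained". Using the Fisher z formula:

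- n = ((1.960 + 0.842) / atanh(r))² + 3.
- With r = 1.5 as printed, atanh is undefined.
- With r = 0.15, n = (2.8016 / 0.15114)² + 3 = 346.6 (345.6 with the small-sample bias term), which matches 346.
- Loss: 346 × 1.05 = 363.3, which matches 363.

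The check below therefore uses n = 346.

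**Pool size (an assumption).** The plan does not give it. The visible part of the data form, printed under section 20, offers:

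- age, sex and admission type: 3;
- admitting diagnosis: 11 groups, which is one factor or 10 indicators under the plan's coding rule;
- chronic diseases: 17 top-level items, or 21 if the device and haematological sub-items replace their two headings;
- APACHE II: 1.

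This gives 3 + 1 + 17 + 1 = 22 variables, 3 + 10 + 17 + 1 = 31 terms, or 3 + 10 + 21 + 1 = 35 terms. Removing atrial fibrillation/flutter and morbid obesity from the 31, because of the exclusion criteria, leaves 29.

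**Chance of keeping at least one noise predictor when all k candidates are null.** For independent tests this is 1 − 0.95^k. Simulated backward deletion at 0.05 with n = 346 gives nearly the same. The simulated ranges cover separate runs with different assumed predictor types, prevalences and correlations.

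| k | 1 − 0.95^k | Simulated backward deletion |
|---|---|---|
| 5 | 23% | 21-24% |
| 10 | 40% | 39-42% |
| 14 | 51% | 51% |
| 22 | 68% | 68% |
| 29 | 77% | 77% |
| 31 | 80% | 80-82% |
| 35 | 83% | 84-86% |

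The chance first passes one half at k = 14 (k = 13 gives 49%). With 35 null terms, about 2.0 are kept on average and the apparent R-squared is about 3.0%.

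**Is deletion the cause?** Fitting all 35 null terms once, with no deletion, gives at least one P<0.05 in 85% of runs, against 86% with deletion. The number of tests drives the rate.

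**Optimism of fit.** Assumed scenario: n = 346, 5 true effects of 0.13 SD and 30 noise terms. Three separate simulations of the rule gave R-squared of 10.3%, 10.4% and 10.6% in the study data, against 1.6%, 1.8% and 1.4% in new patients.

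**What an adjustment would do.** As an illustration, a retention threshold of 0.05/k brings the chance of any noise factor to 4-6% in simulation (4.9% by formula).

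**The case against.** **The pool is not known.** Nothing says that every item on the form enters this model, and the form text available here ends at APACHE II. Exclusions would thin some items. With 5 to 10 candidates the chance is 23-40%. A reader might infer from the form that noise will usually be reported, but that needs about 14 or more null candidates, and the documents establish no number. This stands, and it is why a range is given. It does not rescue the rule: with no fixed list, the error rate cannot be bounded at all.

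**All candidates null is a benchmark, not a forecast.** This also stands. But if 8 of 22 variables truly mattered, the other 14 would still give 51%.

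**Deletion is not the main fault.** Correct, as the single full fit shows. A reader might also infer that deletion ruins interval coverage, by setting about 65% for retained terms against 95% for a full model. Those figures have different denominators: significant survivors in one, all terms in the other. A noise term kept at P<0.05 has a 95% interval that excludes zero by construction. Compared like with like, significant terms in the full model cover 64-65% and their true effects are inflated by 27%; under deletion the figures are 63% and 24%. No claim of lost coverage from deletion is made here.

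**Goal 3 concerns factors affected by blood pH.** Age, sex and pre-existing disease are not such factors, so the form's items are largely not the pool that goal 3 calls for. This stands and shapes the fix.

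**The plan does not say that it will report R-squared.** True. The optimism applies if fit is reported, as is usual for a predictive model.

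**Conclusion.** The point holds in limited form. As written, the rule gives an uncontrolled and unreported chance of naming at least one false factor: about 23% with 5 null candidates, 51% with 14, 68% with 22 and 80-86% with 31-35. Any reported fit would be optimistic, at about 10% apparent against 1-2% in new patients in the assumed scenario.

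These figures rest on n = 346, on all candidates being null for the first set, on assumed effects and prevalences, and on a pool size inferred from the form.

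It would be wrong to infer that the primary pH result is compromised. The pH-effect model is a separate regression with its own retention rule, and nothing here changes its coefficient. Because the model serves a secondary objective of an observational study, this is a cheap improvement and not a condition for the study's validity.

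**What to change.** Before analysis, list the candidate predictors of contractility in the SAP. Choose them on physiological grounds and include the pH-affected factors that goal 3 asks about. Then do one of two things:

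- fit the listed terms once, report every coefficient with its interval, and apply a stated multiplicity adjustment before any term is named as a factor; or
- keep the backward selection, but bootstrap the whole procedure and report inclusion frequencies and an optimism-corrected R-squared. The manual steps would first have to be written as a fixed rule that can be repeated in each resample.

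In either case, state how many candidates were examined and label the result exploratory.

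A shorter list alone is not enough: 12 null terms each tested at 0.05 still give 1 − 0.95^12 = 46%.

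The cost is SAP wording and some analysis code, with no extra patients or data. The downside is fewer declared factors and a lower reported R-squared.
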